6.4 Endpoint Assessment

The primary outcome (primary endpoint) will be control of outbreak, defined as no new cases of COVID-19 in residents for 24 consecutive days up to day 40 after the start of prophylaxis. This outcome is dichotomous (yes/no) and will be determined at the level of the cluster (LTCH unit).

Secondary outcome measures (endpoints) are:

- 1. The proportion of residents of included LTCH units who die up to day 40, and up to day 60
- 2. The proportion of residents of included LTCH units who were uninfected at baseline and develop new symptomatic microbiologically confirmed COVID-19 up to day 40
- 3. The proportion of exposed staff uninfected at baseline in whom SARS-CoV-2 infection is identified up to day 14 and up to day 40
- 4. The proportion of residents of included LTCH units hospitalized up to day 40
- 5. The proportion of residents of included LTCH units who discontinue study medication due to adverse events
- 6. The proportion of LTCH staff of included LTCH units who discontinue study medication due to adverse events.
- 7. The occurrence of new microbiologically confirmed COVID-19 infections in residents in other units of the facility up to day 40 (dichotomous, at LTCH level)
- 8. The proportion of previously unaffected LTCH units of the remainder of the facility in which a case of COVID-19 is identified
- 9. The proportion of residents in the remainder of the facility who develop COVID-19 infections up to day 40

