14.1.2 Serious Adverse Events (SAEs)

A SAE is defined as an AE meeting one of the following criteria at any dose:

- Results in death during the period of protocol-defined surveillance
- Is a life-threatening event (defined as a participant at immediate risk of death at the time of the event)
- Results in in-patient hospitalization or prolongation of existing hospitalization during the period of protocol-defined surveillance
- Results in persistent or significant disability or incapacity (disability is defined as a substantial disruption of a person's ability to conduct normal life functions)
- Is a congenital anomaly or birth defect

Any other important medical event that may not result in one of the above outcomes, may be considered a SAE when, based upon appropriate medical judgment, the event may jeopardize the participant and may require medical or surgical intervention to prevent one of the outcomes listed above. Examples of such medical events include allergic bronchospasm requiring intensive treatment in an emergency room or at home, blood dyscrasias or convulsions that do not result in in-patient hospitalization, or the development of drug dependency or drug abuse.

Participants will be monitored during the 60-day study period for SAEs. If an SAE is ongoing at the time a participant discontinues/completes the study, the SAE will be followed until the Investigator agrees that the event is satisfactorily resolved, becomes chronic, or that no further follow-up is required.

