Unlikely: A clinical event, including an abnormal laboratory test result, whose temporal relationship to Investigational Product administration makes a causal relationship improbable (e.g., the event did not occur within a reasonable time after administration of the trial medication) and in which other products or chemicals or underlying disease provides plausible explanations (e.g., the participant's clinical condition, other concomitant treatments).

Not related: The AE is completely independent of Investigational Product administration, and/or evidence exists that the event is definitely related to another etiology. There must be an alternative, definitive etiology documented by the clinician.

All SAEs which occur during the course of the study must be reported to the Project Manager within 24 hours of the site becoming aware of the event. The Project Manager will be responsible for reporting SAEs to Health Canada on behalf of the Sponsor. SAEs will be reported to:

Project Manager: [name], CCRP, PMP

[contact] [name]

[contact]

E-mail: [contact]

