15.3.2 Analysis of Secondary Outcome Measures

Secondary analyses will include generalized linear mixed models (GLMMs) with logit link to estimate the effect of favipiravir on the probability of the secondary outcomes at participant level, while accounting for clustering of participants in LTCHs. We will also compare the onset of symptomatic disease, hospitalization, and mortality in time-to-event models. All analyses will be by intention-to-treat.

Safety outcomes will include the number of serious adverse events in residents and staff, and the proportion of residents and staff whose study medications are discontinued due to adverse events

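### The SAE safety outcome is an undivided count that takes in the resident deaths and hospitalizations used as efficacy outcomes, so a small to moderate excess of drug-caused SAEs can be offset or lost

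*Protocol*

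**What the plan says.** Section 15.3.2 states: "Safety outcomes will include the number of serious adverse events in residents and staff". The same sentence names a second safety outcome, the proportion of residents and staff who stop study medication because of adverse events. The SAE outcome is not restricted by cause or by relation to the drug, and residents and staff are named together.

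Section 14.1.2 sets the seriousness criteria. Two of them are "Results in death during the period of protocol-defined surveillance" and "Results in in-patient hospitalization or prolongation of existing hospitalization during the period of protocol-defined surveillance". Neither excepts COVID-19 or events that are study outcomes. On the window it says "Participants will be monitored during the 60-day study period for SAEs".

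Section 6.4 lists as secondary outcome 1 "The proportion of residents of included LTCH units who die up to day 40, and up to day 60" and as outcome 4 "The proportion of residents of included LTCH units hospitalized up to day 40". Both are all-cause and concern residents only. Section 15.3.2 adds: "We will also compare the onset of symptomatic disease, hospitalization, and mortality in time-to-event models".

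On causality, section 14.2 has investigators grade every collected adverse event, serious ones included. Section 14.1.1 carries a bracketed remark that confines the causality assessment to the investigational arm.

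**The concern.** For participating residents, an adverse event that ends in death by day 60 or in admission by day 40 enters both the efficacy comparison and the SAE count. Units are eligible only with an active outbreak (7.1.1), so disease events are built into that count.

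Two consequences follow. If favipiravir prevents infections, its arm loses COVID-19 SAEs, and that loss can cancel SAEs the drug causes. If it prevents nothing, the difference between arms depends heavily on which of the 8 units per arm had large outbreaks, and a modest excess is hard to see.

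This matters because residents are frail and the planned course of 25 days (10.1) is longer than the 22 days cited as previously studied (4.3, 10.1.1). SAE data that can be read separately from efficacy would be useful.

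**Working it through.** **The plan's own figures.** The protocol gives no expected SAE rate and no power for SAEs. Its only power figure is more than 85% for the primary outcome (15.2). Exact enumeration for Fisher's two-sided test with 8 units per arm, 12.5% against 87.5%, gives 87.0%, which agrees. It says nothing about safety.

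**Inputs from the protocol**
- Units of 16 to 32 residents (7.1.1), 8 per arm, so 128 to 256 residents per arm. I assume 24 per unit: 8 × 24 = 192.
- Attack rate: median 35%, range 13% to 49% (influenza in long-term care), and up to 70% in explosive respiratory outbreaks (15.2).
- COVID-19 case fatality: 33.7% in one care home (15.2); 14.8% at age 80 and over (4.1).
- Reduction in cases with prophylaxis: 55% (influenza, 15.2).

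**Offset from deaths alone**

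COVID-19 deaths counted as SAEs = residents × attack rate × case fatality.
- Placebo: 192 × 0.35 × 0.337 = 22.6
- Favipiravir: 22.6 × (1 − 0.55) = 10.2
- Offset: about 12.5 events; 0.35 × 0.337 × 0.55 = 6.5% of residents

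At that level of drug-caused SAEs the two arms would show equal totals. The ends of the range:
- Low: 0.13 × 0.148 × 0.55 = 1.1%
- High: 0.70 × 0.337 × 0.55 = 13.0%

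Two simplifications pull in opposite directions. COVID-19 hospitalizations are left out because the protocol gives no rate; they would enlarge the offset. All cases are treated as preventable, although units enter with 2 to 4 cases. Removing 2 of 24 residents gives (0.35 − 0.083) × 0.337 × 0.55 = 4.9%, and removing 4 of 24 gives (0.35 − 0.167) × 0.337 × 0.55 = 3.4%. On the same logic the low end would move towards nil.

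**Simulation of both directions**

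20,000 trials, 8 units of 24 per arm, unit attack rate uniform from 13% to 49%, case fatality 33.7%. The background SAE risk (2%) and the drug-caused SAE risk (2%, 5%, 10%) are assumptions. Power is the chance that a t-test on unit counts gives p < 0.05 with more SAEs on favipiravir.

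| Drug-caused SAEs | Reduction in cases | Mean excess, all SAEs (95% range) | Chance favipiravir shows more | Power, all SAEs | Power, non-COVID SAEs |
|---|---|---|---|---|---|
| 2% | none | +3.9 (−11 to 19) | 0.68 | 0.07 | 0.18 |
| 2% | 55% | −7.2 (−20 to 6) | 0.12 | 0.00 | 0.18 |
| 5% | none | +9.7 (−6 to 25) | 0.88 | 0.21 | 0.60 |
| 5% | 55% | −1.4 (−15 to 12) | 0.39 | 0.02 | 0.60 |
| 10% | none | +19.2 (3 to 36) | 0.99 | 0.57 | 0.96 |
| 10% | 55% | +8.2 (−7 to 23) | 0.85 | 0.18 | 0.96 |

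With attack rates from 13% to 70% and 5% drug-caused SAEs, power on all SAEs is 0.16 (no reduction) and 0.01 (55% reduction), against about 0.60 on non-COVID SAEs. The last column assumes perfect attribution and no clustering of other SAEs, so it is a best case. Even then a 2% excess would usually be missed.

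**The case against.** The strongest reply is that this is analysis-plan territory. Section 15.3.2 uses open wording that allows further safety outcomes, and an analysis plan not at hand could split SAEs by cause. The raw material is also planned: events are classified by relatedness and expectedness (13.3 Medical Oversight), physicians are asked whether COVID-19 is a possible diagnosis (12.1), residents who die in the home are swabbed (12.2.1), and the DSMC reviews all resident deaths (17.2.1). Part of this stands, since a later split is not excluded. But the outcome that the protocol does state makes no use of the grading, blind attribution has to be recorded as events occur, and 14.1.1 conflicts with 14.2 and with the blinding in 9.2 on whether the placebo arm is graded at all.

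A second reply is that all-cause SAEs by arm are a conventional measure of net harm, and that excluding COVID-19 events conditions on something that happens after randomization and that the drug may change. It could also discard harm in infected residents, who also receive study drug. This stands, and it is why the new line must be added and not substituted. Staff SAEs duplicate no death or hospitalization outcome, so the overlap concerns residents only.

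Three stronger readings are tempting but unsupported:
- A reader might infer that the SAE count is the trial's principal safety measure. The protocol does not rank it so, and discontinuation for adverse events stands beside it.
- A reader might infer that a resident admitted who then dies is counted twice. Section 14.1.2 defines an SAE as an adverse event meeting a criterion, and one event can meet several; no counting rule makes it two.
- A reader might infer that no safety conclusion is possible. The table shows a large excess weakened but still visible in most trials.

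**Conclusion.** The overlap is plain in the text: the stated SAE outcome is undivided, and for residents it includes events that are also compared as efficacy. On the protocol's central figures and 192 residents per arm, prevented deaths alone could offset drug-caused SAEs in about 6.5% of residents, or about 12 events (1.1% to 13.0% over the attack rates and fatalities the protocol cites). If the drug does not work, a 5% excess is detected with power of about 0.21.

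The direction of the problem follows from the definitions. Its size rests on influenza attack rates and an influenza effect, on assumed unit size, background and drug-caused SAE risks, and on treating all cases as preventable. The conclusion is limited to small and moderate excesses in residents. It is worth correcting because a better outcome costs little.

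**What to change.** - In 15.3.2, keep the all-SAE outcome. Add the number and proportion of participants with at least one SAE other than death or hospitalization due to microbiologically confirmed COVID-19, by arm and separately for residents and staff.
- Have the attribution made blind to allocation, in both arms, by the investigator who already classifies events under 13.3 Medical Oversight.
- Reconcile 14.1.1 with 14.2 so that causality is graded in both arms.
- Give the DSMC both lines.

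The cost is a short addition to 15.3.2, one yes/no field on the SAE form and a correction in 14.1.1. The downside is that attribution needs judgement and the new line conditions on a post-randomization event, so it supplements the all-SAE count and does not replace it.

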15.3.3 Descriptive analyses

Participant and cluster characteristics will be summarized using appropriate descriptive statistics that account for clustering of participants in LTCHs if necessary. Data from the control arm only will be used to characterize the transmission dynamics and natural history of COVID-19 among LTCH in the Canadian context, including estimation of the secondary attack rate in roommates and unit mates, clinical features of COVID-19 in LTCH residents and symptom burden.

15.3.4 Subgroup Analyses

No subgroup analyses will be performed.

16. ETHICAL CONDUCT OF THE STUDY

This study will be conducted in accordance with the ICH-GCP Guidelines and the principles in the Declaration of Helsinki. Investigators will be thoroughly familiar with the appropriate use of the study drug as described in the protocol and product monograph.

16.1 Informed Consent

Consent and enrolment were described in Section 7.3. Participants may withdraw consent at any time during the course of the study without prejudice. If a participant withdraws from the medication, but consents to be followed-up, the participant will continue to be followed for primary and secondary outcomes.

16.2 Confidentiality

All participant-related information including Case Report Forms, laboratory specimens, evaluation forms, reports, etc. will be kept strictly confidential. All records will be kept in a secure, locked location and only accessible to research staff. Participants will be identified only by means of a coded number specific to each participant. All computerized databases will identify participants by numeric codes only and will be password protected.

Upon request, and in the presence of the investigator or his/her representative, participant records will be made available to the study Sponsor, monitoring groups representative of the study Sponsor, representatives of funding groups, and applicable regulatory agencies for the purpose of verification of clinical trial procedures and/or data, as is permissible by local regulations.

16.3 Institutional Review Board, Ethics Committee, or Research Ethics Board

The REB will review all appropriate study documentation to safeguard the rights, safety, and well-being of the participants. The study will be conducted only at sites where ethics approval has been obtained. A copy of the protocol (including protocol amendments), all versions of informed consent forms, other information to be completed by participants such as survey instruments or questionnaires, and any proposed recruitment materials must be reviewed and approved by the REB of each participating centre prior to implementation of the trial. The investigator will be responsible for obtaining REB approval of the annual Continuing Review throughout the duration of the study. The investigator will notify the REB of serious adverse events as applicable. The investigator will seek prior ethics approval for any protocol deviations except when the change is intended to eliminate an immediate hazard to participants. In this case, the protocol deviation will be promptly reported.

17. GENERAL TRIAL CONDUCT CONSIDERATIONS

17.1 Adherence to Protocol

17.1.1 Protocol Amendments

All protocol amendments will be reviewed and approved and if applicable submitted to the applicable regulatory agencies for prior approval or notification. The Investigator must sign and date the amendment prior to implementation. All protocol amendments must also be submitted to the ethics committee.

17.1.2 Protocol Deviations

No deviations from this protocol will be permitted without the prior written approval of the Sponsor, except when the modification is needed to eliminate an immediate hazard or hazards to participants. Any deviations that may affect a participant's treatment or informed consent, especially those increasing potential risks, must receive prior approval from the REB unless performed to remove an immediate safety risk to the participants. In this case it will be reported to the REB and the Sponsor immediately thereafter. Any departures from the protocol must be documented.

17.2 Monitoring & Auditing

17.2.1 Data Safety Monitoring Committee

The DSMC will include infectious diseases, long term care and public health specialists, at least one biostatistician, and researcher expert in clinical trials. The DSMC will review summary data and all resident deaths after each outbreak, and every 2 months. The purpose of the DSMC will be to review safety concerns and review external data that may have bearing on the design of or decision to continue the trial.

17.2.2 Study Monitoring

Each participating LTCH agrees to allow delegates of the trial data coordination centre to have direct access to the study records and medical records from those patients enrolled in the clinical study as well as Investigational Product accountability records, in order to conduct remote risk-based monitoring of this trial. The proposed remote monitoring scheme will be composed of:

- Review of essential study documents related to participant protection, such as informed consent form signature pages, good clinical practice and protocol training records, delegation log, curriculum vitae and medical license of investigators and Protocol signature page
- 2) Targeted source data verification (SDV) of case report form data will be performed on 5% of participants chosen at random. For residents, this will include medication administration records, faxed line lists of study related data, and, if accessible remotely, nursing notes monitoring symptoms. Only critical data variables identified through risk assessment which are programmed into the electronic data capture system will be source verified.

The Applied Health Research Centre will provide research staff with a form listing key variables for targeted SDV. Sites will be asked to complete the form and send it to the central coordination team, along with de-identified source documents for listed variables/participants via a dedicated end-to-end secure internet portal. Instructions will be provided on how to complete the form, de-identify source documents, and send these documents to the central coordination team using the secure portal.

Upon receipt of the completed form and appropriate source documents, the central coordination team will review these documents to ensure that the data is consistent with the data entered on eCRF. The review will include checking the case report form entries for accuracy and completeness against source documents. Applied Health Research Centre or delegates will maintain a monitoring log of all patients for whom source documents are requested, received, and verified. Variables will be marked as "verified" in the monitoring log once the review is complete. Urgent issues will be communicated on an ongoing basis as needed with the PIs/Sponsor.

If errors or inconsistencies are noted, a follow up email will be sent to the Principal Investigator and Primary Study Coordinator. The follow up email will include a summary of the issues identified, outline of any corrective actions and/or request an explanation, and a timeline for resolution.

17.3 Record Keeping

17.3.1 Data Collection

The Investigator must maintain detailed records on all study participants. Data for this study will be recorded in the participant's chart and entered into case record forms. Applicable data from the participant's chart should be recorded in the case record forms completely and promptly, taking time to correct any mistakes. Copies of case record forms will remain at the clinical site at the conclusion of the study.

17.3.2 Source Documents

The Investigator must maintain adequate and accurate source documents upon which case record forms for each participant are based. They are to be separate and distinct from case record forms except for cases in which the Sponsor has pre-determined that direct data entry into specified pages of the participant's case record forms is appropriate. These records should include detailed notes on:

- Oral and written communication with participant regarding the study treatment (risks/benefits)
- Participation in trial and signed and dated informed consent forms
- Inclusion and exclusion criteria details
- Visit dates
- Adverse events and concomitant medication
- Laboratory result printouts
- Participant's exposure to any concomitant therapy
- Reason for premature discontinuation (if applicable)
- Enrollment number
- Adherence with the study protocol and protocol deviation information

17.3.3 Data Corrections

Any corrections of data entered on source documents at the LTCH unit should be crossed out with a single horizontal line, initialed and dated.

17.3.4 Data Management

Data management responsibilities for this trial will be assumed by the Applied Health Research Centre. Instructions concerning the recording of study data on case record forms will be provided in a comprehensive study Operations Manual. Detailed aspects of data handling will be described in the Data Management Plan.

17.3.5 Record Retention

The Investigator will maintain all study records according to the ICH-GCP and applicable Health Canada regulatory requirements. Records will be retained for 25 years, in accordance with applicable Health Canada regulatory requirements. If the Investigator withdraws from the responsibility of keeping the study records, custody must be transferred to a person willing to accept the responsibility and the Sponsor-Investigator notified. The Investigator should ensure that no destruction of medical records occurs without the written approval of the Sponsor-Investigator.

17.4 Steering Committee

The steering committee (SC) will include: [name], [name], [name], [name], [name], and [name]. The SC will meet 1-2 times monthly to discuss epidemic trends/recruitment, consider new sites, ethical issues, and emerging scientific or logistical issues. The steering committee will be advising the sponsor. Final decision-making authority will rest with the sponsor.

18. DISCLOSURE AND PUBLICATION POLICY

18.1 Publication of Study Results

Following completion of the study, the lead Principal Investigator is expected to publish the results of the primary and secondary analyses from this trial in peer-reviewed scientific journals. A detailed authorship policy will be developed and agreed upon by all investigators to determine how best to fairly acknowledge the contributions of relevant parties.

